After providing informed consent, subjects will be screened for eligibility within 28 days prior to Day 1 (first day of dosing). Subjects may be rescreened once based on the clinical judgment of the investigator in collaboration with the sponsor or designee. The screening period may be extended by up to 14 days in extenuating circumstances in consultation with the Sponsor or designee.

Eligible subjects will return to the study site on Day 1 for baseline assessments. Randomized subjects will receive a loading dose of 160 mg (consisting of four 40 mg tablets) in the clinic on Day 1 and subsequently 80 mg (consisting of two 40 mg tablets) once weekly (Weeks 2 to 8) thereafter or matching placebo. Subjects will also receive their second (Day 8), and fifth (Day 29) doses of study treatment at the study site in order to obtain ECG and PK pre- and post-dose assessments. Subjects will be instructed to take study treatment orally on the same day

each week (with or without food) and will be released from the study site after completion of all study assessments with sufficient study treatment supply between study visits. Compliance with study treatment will be assessed throughout the study. Subjects will have onsite and virtual study visits during the Treatment Period and complete study assessments as shown in the schedule of assessments (Table 8).

Subjects who discontinue study treatment should not be automatically withdrawn from the study prior to completion of Day 57 assessments, regardless of study treatment compliance, unless consent for study participation has been withdrawn (Section 8.1).

Subjects who withdraw from the study early will be asked to return to the study site for an Early Termination (ET) Visit and, unless consent has been withdrawn, will be asked to come back approximately 4 and 8 weeks after their last study treatment for Safety Follow-Up visits.

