8.1. Discontinuation of Study Treatment

If a subject prematurely discontinues study treatment, the investigator will record the reason for discontinuation on the relevant eCRF. Data for any outcome measures, particularly the primary and secondary endpoints, as well as safety follow-up, are important to collect. Subjects will not be automatically withdrawn from the study and should continue participation in the study, regardless of study treatment compliance, unless consent for study participation has been withdrawn. For any subsequent study visits after study treatment is prematurely discontinued, subjects should have 1 final PK sample collected (ie, subsequent PK samples are not required); however, subjects should continue with study assessments at the study site or with virtual visits.

If medically indicated, treatment with medication listed under Section 7.1 is no longer prohibited after study treatment discontinuation.

Reasons for discontinuation from study treatment include but are not limited to:

- Withdrawal by subject
- Death
- Lost to follow-up

- Site termination by the Sponsor
- Study termination by the Sponsor
- AE
- Pregnancy
- Lack of efficacy
- Protocol deviation
- Investigator decision
- Sponsor decision

The investigator must discontinue study treatment if the subject experiences any of the following:

- If the type, frequency, or severity of any AE becomes unacceptable/intolerable
- If the subject is unable to tolerate the lowest allowable dose (80 mg or placebo)
- QTcF of >500 msec (cardiologist verified) on any ECG tracing
- If the subject is confirmed to be pregnant
- Withdrawal of consent for study treatment administration by subject
- If the subject exhibits suicidal behavior, or suicidal ideation of type 4 (active suicidal ideation with some intent to act, without specific plan) or type 5 (active suicidal ideation with specific plan and intent) based on the C-SSRS or according to the investigator's clinical judgement
- Study treatment should be discontinued with appropriate clinical follow-up (including repeat laboratory tests) until a subject's laboratory profile has returned to normal/baseline status), if any of the following occur (see Appendix D for additional detail):
 - ALT or AST $>8 \times ULN$, or
 - ALT or AST >5×ULN and persists for more than 2 weeks, or
 - ALT or AST >3×ULN in conjunction with elevated total bilirubin >2×ULN or INR >1.5

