5.6. Visit Windows

Study day is calculated relative to the date of the Day 1 visit. For efficacy data analysis, the nominal visit number for each visit, including scheduled and early termination/end of study visits will be re-mapped based on the actual study day according to Table 1.

Table 1: Analysis Visit Windows for Efficacy Analysis

Scheduled Visit	Target Study Day	Analysis Window (Analysis Day Range)
Baseline	1	1
Day 29	29	2-43
Day 57	57	44+

For safety data analysis, the nominal visit number for each visit, including scheduled, unscheduled, repeated and early termination/end of study visits, will be re-mapped to an analysis visit according to Table 2: Analysis Visit Windows for Safety Analysis

.

Neurocrine Biosciences, Inc. Statistical Analysis Plan Study NBI-1065846-MDD2020 16August2023

Table 2: Analysis Visit Windows for Safety Analysis

Scheduled Visit	Target Study Day	Analysis Window (Analysis Day Range)
Baseline	1	1 prior to first dosing
Day 1 Post Baseline	1	1 post first dosing
Day 8	8	2-15
Day 22	22	16-25
Day 29	29	26-36
Day 43	43	37-50
Day 57	57	51-last dose day
Day 78	Last dose day+28	Last dose day+1-last dose day+42
Day 106	Last dose day+56	last dose day+43+

If multiple measurements occur within the same visit window after mapping, the measurement that is closest to the target study day will be used for the summary tables where one observation per visit is needed, unless otherwise specified. Where there are ties between the earlier and later observation within the visit window, the earlier observation will be used.

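### In SAP Table 2 the Day 8 to Day 43 safety windows are not limited by the last dose, so for early treatment stoppers one record can fit both a treatment-period row and a follow-up row, with no rule to choose

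*SAP*

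**What the plan says.** SAP Section 5.6 maps safety data by Table 2. All nominal visits, "including scheduled, unscheduled, repeated and early termination/end of study visits, will be re-mapped to an analysis visit", so the intention is one row per record. Four rows have fixed study-day limits: Day 8 (2-15), Day 22 (16-25), Day 29 (26-36) and Day 43 (37-50). The other three depend on the last dose. The Day 57 row is "51-last dose day", the Day 78 row is "Last dose day+1-last dose day+42" with its target at last dose plus 28 days, and the Day 106 row starts at "last dose day+43" and is open-ended.

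One selection rule follows the table: "If multiple measurements occur within the same visit window after mapping, the measurement that is closest to the target study day will be used", with ties going to the earlier observation.

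The protocol keeps people who stop study treatment under observation. Section 4.1: "Subjects who discontinue study treatment should not be automatically withdrawn from the study prior to completion of Day 57 assessments". Section 8.1: "Subjects will not be automatically withdrawn from the study and should continue participation in the study, regardless of study treatment compliance". The schedule of assessments (protocol Table 8, footnote c) also places early termination (ET) assessments 7 days (±2) after the final dose.

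**The concern.** The fixed rows and the last-dose rows use different clocks. They fit together when the last dose is on Day 50, as planned, and overlap when it is earlier. A subject whose last dose was on Day 8 and who attends Day 29 has a record inside the Day 29 row and also inside the Day 78 row (Days 9-50). The selection rule chooses among several records in one window. It says nothing about one record in two windows.

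The programmer must then choose a row, or let the record appear in both, which contradicts the single assignment that the text intends. A post-dose value may be shown under a treatment-period visit, a follow-up visit, or both. The protocol's stopping rules include liver tests, QTcF and suicidality, so some of these records may matter to a safety reader. The arms have about 44 subjects each, so a few records can move a by-visit summary.

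**Working it through.** **Inputs.** Windows: SAP Table 2. Planned doses: Days 1, 8, 15, 22, 29, 36, 43 and 50 (protocol Section 6.2). Content of visits: protocol Table 8. Days 22 and 43 are virtual and carry no laboratory tests, vital signs or ECG. Day 8 carries laboratory tests and vital signs. Day 29 carries laboratory tests, vital signs and ECG.

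**The plan's own figures.** With last dose L = 50, the follow-up targets are 50 + 28 = 78 and 50 + 56 = 106, which match the row labels. The Day 78 window is Days 51-92 and does not touch the fixed rows.

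**Overlap.** The fixed rows cover Days 2-50 without a gap, and the follow-up rows cover every day from L + 1. Every day from L + 1 to 50 therefore lies in two rows, which is 50 − L days.

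| Last dose L | Day 78 window | Days in two rows | Scheduled visits in two rows | With labs and vitals | With ECG | ET at L+7, rows |
|---|---|---|---|---|---|---|
| 1 | 2-43 | 2-50 (49) | 8, 22, 29, 43 | 8, 29 | 29 | Day 8: rows 8 and 78 |
| 8 | 9-50 | 9-50 (42) | 22, 29, 43 | 29 | 29 | Day 15: rows 8 and 78 |
| 15 | 16-57 | 16-50 (35) | 22, 29, 43 | 29 | 29 | Day 22: rows 22 and 78 |
| 22 | 23-64 | 23-50 (28) | 29, 43 | 29 | 29 | Day 29: rows 29 and 78 |
| 29 | 30-71 | 30-50 (21) | 43 | none | none | Day 36: rows 29 and 78 |
| 36 | 37-78 | 37-50 (14) | 43 | none | none | Day 43: rows 43 and 78 |
| 43 | 44-85 | 44-50 (7) | none | none | none | Day 50: rows 43 and 78 |
| 50 | 51-92 | none | none | none | none | Day 57: row 78 only |

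For L = 1, Days 44-50 are shared by the Day 43 and Day 106 rows, because 1 + 43 = 44. All other overlaps in the table are with the Day 78 row.

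**Totals at nominal visit days.** In two rows: 4 + 3 + 3 + 2 + 1 + 1 = 14, which is every scheduled visit after the last dose up to Day 43. With laboratory tests and vital signs: 2 + 1 + 1 + 1 = 5. With ECG: 1 + 1 + 1 + 1 = 4. The other 14 − 5 = 9 are virtual visits (Day 22 three times, Day 43 six times).

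**Would closeness to target settle it?** Not always, even if the rule were extended across windows. For L = 1, a Day 29 visit is exactly on target for both rows (29, and 1 + 28 = 29). The same holds for L = 15 and a Day 43 visit (15 + 28 = 43).

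**Side note.** A last dose on Day 48 or 49, allowed by the ±2-day dosing window, leaves Days 49-50 or Day 50 in two rows for someone who did not stop early.

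**The case against.** The strongest reply is that the consequence is small, and most of that reply stands. Nine of the 14 visits are virtual, with C-SSRS as their only safety scale. SAP Section 9.8.1 pools C-SSRS over all postbaseline assessments and uses the maximum score for its shift tables, so those outputs do not depend on Table 2. QTcF categories use the highest postbaseline value, laboratory shift tables use baseline and Day 57, adverse events are classified by onset, and efficacy has its own windows in Table 1. What remains is descriptive, with no hypothesis test.

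Stronger readings are tempting and are not supported:

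- A reader might infer that a value taken one day after the last dose will be shown as 4-week follow-up. The window permits it, but the closest-to-target rule makes it unlikely. At nominal scheduled visits, the laboratory or vital-sign record chosen for the Day 78 row is at least 14 days after the last dose for every planned L from 1 to 43 (for example, Day 29 at +28 for L = 1 and Day 57 at +35 for L = 22).
- A reader might infer that those affected mostly stopped for safety reasons. Protocol Section 8.1 lists many reasons and gives no frequencies.
- A reader might infer that Table 2 contaminates a defined on-treatment analysis. The SAP plans no such by-visit analysis. The division into treatment-period and follow-up rows comes from the protocol schedule.

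It can also be said that assigning each visit to a single row rules out double counting. That shows the intention but does not say which row is meant.

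**Conclusion.** The concern holds in a limited form. For any last dose before Day 50, Table 2 gives a post-dose record two rows where the text intends one, and neither the SAP nor the protocol resolves it. This is a conflict within a stated rule, not merely missing detail, and the protocol's retention of treatment stoppers makes such records likely.

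The size is modest: 5 scheduled visit patterns with laboratory tests and vital signs, 4 with ECG, and the ET visit at 7 days for every planned last dose from Day 1 to Day 43. These counts assume visits and doses on their nominal days.

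The documents give no rate of stopping treatment while staying in the study. If it were 5% to 15% of 88, there would be 0.05 × 88 = 4.4 to 0.15 × 88 = 13.2 such subjects, or about 4 to 13. That is an upper limit on those affected, not an estimate. Among those who stay on the schedule, a last dose on Day 29 or 36 involves only the virtual Day 43 visit, and a last dose on Day 43 involves no scheduled visit.

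The by-visit safety tables should be made unambiguous before database lock, which is when SAP Section 1 commits to having all analysis decisions made. The primary result is not at risk.

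**What to change.** Add a note to Table 2 that makes the rows mutually exclusive under one stated precedence. A workable version:

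- Scheduled Day 8 to Day 57 visits attended by subjects still in the study map by study day to the treatment-period rows.
- The ET visit maps to one named row.
- Only designated safety follow-up visits, about 4 and 8 weeks after the last dose, map to the Day 78 and Day 106 rows. If one attendance serves as both a scheduled and a follow-up visit (as at Day 29 for L = 1), the note names the row that takes it.
- Unscheduled records follow one stated cut-off relative to the last dose.
- Records after the last dose are flagged, so that by-visit summaries can be shown with and without them.

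Write this together with a corrected upper limit for the Day 57 row. With the planned last dose on Day 50 that window runs from 51 to 50 and is empty, so a Day 57 visit falls into the Day 78 row (Days 51-92). Correcting that limit alone leaves the overlap on Days 2-50 in place.

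Two simpler rules have drawbacks. Admitting only records after the Day 57 visit to the Day 78 row empties that row for anyone with a last dose on or before Day 15 who attends Day 57, because 15 + 42 = 57. Capping the four fixed windows at the last dose day does put every study day from 2 onward in exactly one row (checked for last doses on Days 1 to 52), but it sends every post-dose scheduled visit to the follow-up rows and does not repair the Day 57 row.

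The cost is one table note and a programming rule, with no change to data collection or trial conduct.

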Virtual Visit				X		X			
AE assessment	X	X	X	X	X	X	X	X	X
Concomitant medications	X	X	X	X	X	X	X	X	X
Schedule exit interview							X		

AE=adverse event; ; CGI-S= Clinical Global

Impression – Severity; C-SSRS=Columbia-Suicide Severity Rating Scale; DARS=Dimensional Anhedonia Rating Scale; ECG=electrocardiogram; ET=early termination; FSH=follicle-stimulating hormone; HAM-D17=Hamilton Depression Rating Scale-17; MADRS=Montgomery-Åsberg Depression Rating Scale; MGH-ATRQ=Massachusetts General Hospital - Antidepressant Treatment Response Questionnaire; MINI=Mini-International Neuropsychiatric Interview; PCRS=Placebo-Control Reminder Script;

PK=pharmacokinetics;

; SAFER= State versus Trait, Assessability, Face Validity, Ecological Validity,

Rule of Three P's; SHAPS=Snaith-Hamilton Pleasure Scale W=week

- ^a Subjects will undergo screening procedures that may be completed in 1 or more visits during the Screening Period of up to 4 weeks. Subjects may be rescreened once based on the clinical judgment of the investigator in collaboration with the sponsor or designee. The screening period may be extended by up to 14 days in extenuating circumstances in consultation with the Sponsor or designee.
- ^b Assessments on Day 1 should be performed prior to study treatment administration.
- ^c Subjects will return to the clinic approximately 4 and 8 weeks following their final dose for safety follow-up or 7 days (±2) for the ET visit assessments if the subject discontinues study treatment or withdraws consent to participate in the study.
- d After consent is obtained, the registry database check should be performed as early as possible at the screening visit to avoid unnecessary procedures.
- ^e Height will be collected at screening only.
- f Triplicate 12-lead ECGs will be performed (at least 1 minute apart and within 15 minutes) after the subject has rested supine for at least 5 minutes on screening, Day 1, Day 29, and Day 57 or ET visit. On Day 1 and Day 29, ECGs will be performed at predose and 2 hours postdose. ECGs are also needed on Day 78 and Day 106 if ECG(s) during the Treatment Period were abnormal.
- g Vital signs will be measured for the following: orthostatic systolic and diastolic blood pressure, orthostatic pulse rate, respiratory rate, and body temperature. The same method should be used to take body temperature throughout the study.

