5.5. Study Day

Study day will be calculated relative to the date of the first study treatment (Study Day 1) for dates on or after Day 1:

Study Day = Date of Interest – Date of Study Day 1 + 1

Study day will be calculated relative to Study Day 1 for dates before Day 1:

Study Day = Date of Interest – Date of Study Day 1

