9.7. Electrocardiogram (ECG)

The triplicate values of the quantitative ECG variables (heart rate, PR interval, QRS duration, QT interval, and corrected QT interval using Fridericia's formula [QTcF]) measured at each visit will be averaged for the purpose of analysis. For the categorical ECG interpretation variable (the investigator's assessment of the ECG as "Normal", "Abnormal, not Clinically Significant", or "Abnormal, Clinically Significant"), which is also reported in triplicate, the value that represents the greatest degree of abnormality will be used in all summary tables. If less than 3 values are recorded at an assessment, then the average/greatest abnormality of the available value(s) will be used.

The quantitative ECG variables will be summarized with descriptive statistics by treatment group at baseline and at each scheduled postbaseline visit through follow-up visit. Both observed values and changes from baseline will be summarized. Frequency counts and percentages for the ECG interpretation variable categories will be summarized at each scheduled visit.

Categorical summaries will be presented for the QTcF interval data. For these summaries, a subject's highest reported postbaseline value (including values reported at unscheduled visits) will be used to determine in which category(s) the subject will be counted. The averaged triplicate values will be used when determining each subject's highest reported values.

Two categorical summaries will be presented for the QTcF intervals. For the first summary, the number and percentage of subjects in each treatment group whose highest reported QTcF postbaseline value meets the following thresholds will be summarized:

Neurocrine Biosciences, Inc. Statistical Analysis Plan Study NBI-1065846-MDD2020 16August2023

- Greater than 450 msec
- Greater than 480 msec
- Greater than 500 msec

The second categorical summary will display the number and percentage of subjects in each treatment group whose largest QTcF increase from their baseline value meets the following thresholds:

- Greater than 30 msec
- Greater than 60 msec

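### The SAP's by-visit ECG summaries give no separate Day 29 postdose value, although the protocol schedules one

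*SAP*

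**What the plan says.** **Collection.** Protocol Appendix A, Table 8, footnote f: "On Day 1 and Day 29, ECGs will be performed at predose and 2 hours postdose". Each set is a triplicate. Protocol Section 4.1 explains in-clinic dosing at the second and fifth doses by the need for ECG and PK assessments before and after dosing, so the Day 29 pair is deliberate.

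**Study day.** SAP Section 5.5 counts whole calendar days: "Study Day = Date of Interest – Date of Study Day 1 + 1".

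**Windows.** SAP Section 5.6, Table 2, gives Day 1 two rows, Baseline (before first dosing) and Day 1 Post Baseline ("1 post first dosing"). Day 29 has one row, days 26 to 36, with no split around the dose.

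**Selection within a window.** The observation closest to the target day "will be used for the summary tables where one observation per visit is needed, unless otherwise specified". For ties: "Where there are ties between the earlier and later observation within the visit window, the earlier observation will be used".

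**ECG summaries.** SAP Section 9.7: "The quantitative ECG variables will be summarized with descriptive statistics by treatment group at baseline and at each scheduled postbaseline visit". No time point within a visit is named. Averaging of triplicates is worded per visit, while the rule for incomplete triplicates is worded per assessment: "If less than 3 values are recorded at an assessment".

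**Contrast.** SAP Section 8.1 summarises plasma concentrations by sampling time point as well as by visit.

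**The concern.** ECG values and changes from baseline are a named safety endpoint (Protocol Section 11.4.4, SAP Section 4.4). The protocol brings subjects into the clinic on Day 29 and records a triplicate at a chosen time after the fifth dose. The SAP's window and summary rules, read as written, produce no line for that recording. A reader of the by-visit tables would see the Day 1 postdose mean and one Day 29 mean, and would have no view of average ECG change 2 hours after a repeat dose. The Day 1 split and the PK section show that the SAP distinguishes time points elsewhere. For the Day 29 ECG it does not.

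**Working it through.** The plan states no figure to reproduce on this point. The check applies the SAP's own rules to the protocol's schedule.

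**Step 1: do the two Day 29 sets tie?** The Day 29 visit is allowed ±2 days, so it falls on study day 27 to 31, always inside the 26 to 36 window. Distance to target is |study day − 29|. Both sets are taken on the same date and so share one study day.

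| Visit on study day | Distance, predose | Distance, 2 h postdose | Set kept by the tie rule |
|---|---|---|---|
| 27 | 2 | 2 | predose |
| 28 | 1 | 1 | predose |
| 29 | 0 | 0 | predose |
| 30 | 1 | 1 | predose |
| 31 | 2 | 2 | predose |

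All 5 of 5 permitted days are ties, and predose is kept each time. On Day 1 the two sets map to different rows and both are kept.

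**Step 2: what if the per-visit averaging wording governs?** Let P be the predose triplicate mean and P + d the postdose triplicate mean. Pooling six tracings gives [3P + 3(P + d)] / 6 = P + d/2. The Day 29 mean by reading is then:

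- tie rule: P (none of the shift d is shown)
- pooling: P + d/2 (half of d, not separable)
- separate time points: P and P + d

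Pooling is the less coherent reading. On Day 1 it would mix postdose tracings into a baseline that SAP Section 5.3 defines as before dosing, and Section 9.7 itself speaks of values at an assessment. Averaging within each triplicate fits better, which returns the choice to the tie rule.

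**Step 3: does another scheduled ECG fill the gap?** Table 8 and footnote f schedule ECGs at screening, Day 1, Day 29 and Day 57 (or early termination), plus follow-up only if earlier tracings were abnormal. The last scheduled dose is Day 50 (Protocol Section 6.2), so the Day 57 ECG comes 57 − 50 = 7 days after a dose. Day 29 is therefore the only scheduled 2-hour postdose ECG after Day 1.

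**Step 4: where does the Day 29 postdose value survive?** The categorical QTcF summaries in SAP Section 9.7 (above 450, 480 and 500 msec; increases above 30 and 60 msec) take each subject's highest postbaseline value or largest increase, and are not limited to one value per visit. They use averaged triplicates, so the Day 29 postdose value enters intact under within-time-point averaging and as P + d/2 under pooling. They do not show mean shifts and do not cover PR, QRS or heart rate.

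**Step 5: how many sets?** 88 subjects randomised 1:1 give 88 / 2 = 44 per arm at full attendance. If Day 29 attendance were only the 85% assumed for Day 57, this would be 0.85 × 44 = 37.4, or about 37 per arm.

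**The case against.** The selection rule is conditional: it applies where one observation per visit is needed and nothing else is specified. The SAP never says that ECG tables need one observation per visit. The rule can be read as choosing between competing visits or repeats rather than between two protocol time points, and SAP Section 5.1 promises that all available data will be included in relevant displays. On that view a programmer could tabulate both time points under Day 29, and all that is missing is a clarifying sentence. This shows that the outcome is not certain, but no text in Section 9.7 supports such a layout. Section 9.7 names visits only, and the PK section shows how the SAP writes a summary by time point when it intends one.

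Other parts of the objection stand and limit the point:

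- A reader might infer that the Day 29 postdose data are discarded. They are not: the highest-value QTcF tables can use them. Subject protection does not depend on the by-visit tables either, since the QTcF discontinuation criterion applies to any tracing (Protocol Section 8.1) and clinically significant abnormalities go on the AE form (Protocol Section 9.3.4).
- A reader might infer that the missing value is the one near peak exposure, or that it answers the main ECG question. Neither document gives a time to peak concentration or ranks the ECG questions. The postdose PK windows run from 0.5 to 2 hours and from 2 to 36 hours. The Day 1 postdose ECG, after the loading dose, has its own row, and whether exposure on Day 29 is higher cannot be judged from these documents.
- A reader might count 88 sets as lost. That figure covers both arms; at most about 44 are on active treatment.
- Safety analysis is descriptive, with no hypothesis tests (SAP Section 9), and no efficacy conclusion is affected.

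**Conclusion.** The point holds for the by-visit summaries. As written, the SAP either drops the Day 29 postdose set through the tie rule or pools it with the predose set. In both cases the means and changes from baseline for QTcF, QT, PR, QRS and heart rate contain no separate Day 29 postdose value. The by-visit ECG interpretation categories are affected too if the one-per-visit rule is applied to them. This concerns up to about 44 triplicate sets per arm, and the only 2-hour postdose ECG scheduled after repeated dosing. It is a gap in descriptive safety reporting that is worth closing. It is not a loss of data from the whole analysis.

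Two assumptions matter. First, the QTcF category tables are intact only if triplicates are averaged within time point. Second, the ECG schedule is taken from Table 8 and footnote f, which list no Day 8 ECG, whereas Protocol Section 4.1 gives pre- and postdose ECGs as a reason for in-clinic dosing on Day 8. Those passages should be reconciled. If Day 8 ECG pairs were taken, Day 29 would not be the only repeat-dose postdose ECG, and the single Day 8 row (days 2 to 15) would have the same problem.

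**What to change.** For ECG, split the Day 29 row of SAP Table 2 into Day 29 predose and Day 29 2 h postdose, as Table 2 already does for Day 1. State in Section 9.7 that triplicates are averaged within each time point, so that pooling across the dose is ruled out for both the by-visit and the highest-value tables. Summarise observed values and change from the Day 1 predose baseline for both Day 29 time points.

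The cost is one extra row in the window table and in the ECG summaries. No new data, endpoint or test is needed.
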